## 9.2 STUDY SUBJECT CONFIDENTIALITY

The Investigator must ensure that the privacy of all subjects, including their personal identity and all personal health information, will be maintained at all times. Subjects will not be identified by their names in CRFs or other documents or image material submitted to the Sponsor or designee. Rather, the subject's unique identifier will be utilized.

A subject's Protected Health Information (PHI) will always be treated as confidential. PHI, however, may be reviewed by authorized study staff (e.g., the monitor) to verify data recorded in the eCRFs. The monitor may conduct source-document verification on behalf of the Sponsor, the quality assurance unit, or regulatory authorities.

## 9.3 ELECTRONIC DATA

Electronic data will only be accessible to authorized personnel with a unique user identifier and password for the EDC. Passwords will be set to expire periodically. Access to electronic study data will be provided to research personnel upon completion of training. Read and write access will be provided to investigational sites but only for information and subject data at their site. The CRO will have read-only access and can post queries for potential data-related discrepancies.

## 9.4 PARTICIPATING INSTITUTIONS AND INVESTIGATORS

Study sites and Investigators will be selected based on a variety of factors including, but not limited to, experience with endovascular techniques, access to required facilities and equipment, sufficient and adequately trained personnel, and availability of potential subjects. The criteria used for determination will be documented.

## 9.4.1 INVESTIGATOR RESPONSIBILITIES

Investigator responsibilities include, but are not limited to, the following:

- Conducting the study in accordance with this investigational plan, signed agreement, and applicable regulations protecting the rights and safety of study subjects
- Ensuring that IRB approval is secured prior to starting the study and ensuring continuing review and approval as required throughout the investigation
- Ensuring all associates, colleagues, and employees assisting in the conduct of the study are informed about their obligations, are adequately qualified and trained, and meet their commitments
- Maintaining adequate and accurate records and ensuring those records are available for inspection at any time
- Ensuring that conducting the study does not give rise to a conflict of interest (financial disclosure is required)

# **10 TERMS AND DEFINITIONS**

 Table 10 contains categories, terms, and definitions that are utilized throughout the study and for reporting purposes.

Term or Phrase	Definition
Access site injury requiring intervention, both venous and arterial	An injury to an access site (both venous and arterial) utilized for treatment of PE which requires intervention in order to resolve. This includes for example, an arterial injury associated with ECMO support as part of PE treatment.
Advanced therapy for PE	For the purposes of this study, advanced therapy for low/intermediate- risk PE is considered therapy beyond anticoagulation alone, including: thrombolysis (either systemic or catheter directed), surgical thrombectomy, and percutaneous thrombectomy.
Adverse event (AE)	An Adverse Event (AE) is an untoward medical occurrence or exacerbation of an existing medical condition subsequent to enrollment in the study. AEs are assessed for severity, seriousness, and relationship to thrombus removal therapies/devices/procedures.
	The study will only capture AEs related to the subject's PE condition and treatment. Reportable AEs include all events considered in the safety analyses, all thrombus removal therapy/device- and/or procedure-related AEs, as well as events resulting in death.
All-cause mortality	Mortality for any reason, does not need to be related to a device, treatment, or pulmonary embolism.
Bailout to an	New need for mechanical circulatory support or another thrombus removal strategy after the
alternative	Primary Treatment strategy was initiated. The additional treatment strategy was not an a
thrombus	priori part of the original treatment plan (conceived beforehand). All bailout events will be
removal strategy	adjudicated by the CEC. See Table 4 for more guidance on bailout events.
Clinical Deterioration	Clinical deterioration is defined as: • Need for CPR
	
 
Need to start IV vasopressors to keep systolic blood pressure > 90 mmHg in a
 

	previously normotensive patient
	
 
Need for mechanical ventilation in a previously spontaneously breatning patient
 
Need for noninvasive positive pressure ventilation in a patient previously on nasal
 

	cannula
	Clinical deterioration occurring after initiation of the Primary Treatment therapy will be adjudicated by the CEC for analysis of the Primary Endpoint.
Context Arm	Context Arm subjects are defined as those subjects with PE who are treated with non- FlowTriever therapies (as the Primary Treatment for PE). Context-Arm therapies may include but are not limited to; thrombolysis (either systemic or catheter directed), anticoagulation, surgical thrombectomy, and non-FlowTriever thrombectomy.
	Endpoints will be evaluated in the Context Arm population in a descriptive manner and will not be used to determine study success.

## Table 10: Terms and Definitions

Term or Phrase	Definition			
Device-related complications	Complications related to devices used for thrombus removal. Complications related to Primary Treatment devices and bailout devices used will be adjudicated by the CEC. Note that complications related to ECMO should be included here where ECMO was part of the Primary Treatment strategy.			
Discharge Location	The location where the patient is discharged from the hospital, may include but not limited to home, home with home healthcare, skilled nursing facility, hospice, etc.			
FlowTriever Arm	FlowTriever Arm subjects are defined as those subjects where FlowTriever is used as the primary thrombus removal treatment for pulmonary embolism. FlowTriever Arm subjects will be the primary population utilized to evaluate the study Primary Endpoints for study success.			
Glasgow Coma	The Glasgow Coma Scale provides a practical method for assessment of impairment of			
Scale	conscious level in response to defined stimuli.			
High-risk Pulmonary Embolism (PE)	
 
Pulmonary embolism with the following signs/symptoms:         
 
Systolic blood pressure <90 mmHg for at least 15 minutes or drop of >40 mmHg in systolic blood pressure for at least 15 minutes, and/or
 
Need for vasopressor support, and/or
 
Resuscitation after cardiac arrest with <30 minutes of CPR and Glasgow Coma Scale >8.
 
 
 
			
Length of Hospital Stay	Time from admission to the hospital for pulmonary embolism treatment until discharge from the hospital post-treatment. For subjects who do not survive until hospital discharge, the length of hospital stay will be from the time of admission until the time of death.			
Length of ICU Stay	Time from admission to the ICU until time of discharge from the ICU. Multiple ICU stays within the same hospital admission (index hospitalization for high-risk PE) will be recorded.			
Major Bleeding, BARC 3b/3c/5a/5b definition	
 
3b: Overt bleeding plus hemoglobin drop of ≥ 5 g/dL (provided hemoglobin drop is related to bleed); cardiac tamponade, bleeding requiring surgical intervention for control (excluding dental/nasal/skin/hemorrhoid); bleeding requiring intravenous vasoactive agents
 
3c: Intracranial hemorrhage (does not include microbleeds or hemorrhagic transformation, does include intraspinal), subcategories confirmed by autopsy or imaging or lumbar puncture, intraocular bleed compromising vision.
 
5a: Probable fatal bleeding; no autopsy or imaging confirmation but clinically suspicious
 
5b: Definite fatal bleeding; overt bleeding or autopsy or imaging confirmation
 
			
Primary Endpoint	
 
In-hospital composite endpoint of:
 
All-cause mortality
 
Bailout to an alternative thrombus removal strategy
 
Clinical deterioration
 
Major bleeding, BARC 3b/3c/5a/5b definition
 
			
Primary Treatment Strategy	The initial treatment strategy for thrombus removal (for the high-risk PE) determined by the treatment team prior to treatment initiation and documented.			
Prior Therapy Arm	Subjects presenting with low/intermediate-risk PE who receive advanced therapy during their hospital stay but subsequently progress to high-risk PE in the same hospital stay should be enrolled in the Prior Therapy Arm.			

Term or Phrase	Definition			
Protocol Deviation	A protocol deviation is a divergence or non-adherence from the protocol-specific study procedures. Protocol deviations should be recorded for all assessments not collected and issues related to eligibility criteria.			
Relatedness of Adverse Event	
 
Unrelated: The clinical event is completely independent of study procedure/study device/study treatment and/or evidence exists that the event is related to another etiology.
 
Related: The clinical event occurs in a plausible time relationship to study procedure/study device/treatment and cannot be explained by any concurrent disease or other devices, drugs or chemicals.
 
Unknown: The relationship to the study procedure/study device/treatment is not known.
 
			
Screen Failure	Patients who do not meet eligibility criteria for enrollment in the study. Screen failure patients will not be entered into the study database/EDC system, and will not be assigned a study subject ID.			
Serious Adverse Event (SAE)	
 
Serious Adverse Event (SAE): An AE which is at least one of the following: 
 
Is fatal
 
Is life-threatening
 
Results in persistent or significant disability/incapacity
 
Results in permanent impairment of a body function or permanent damage to a body structure
 
Results in hospitalization or prolongs a hospitalization
 
Necessitates medical or surgical intervention to preclude permanent impairment of a body function or permanent impairment of a body structure
 
 
 
			
Secondary Endpoints	
 
Secondary Safety Endpoints         
 
Frequency of each primary endpoint composite component
 
Frequency of Stroke (ischemic or hemorrhagic)
 
Frequency of device-related complications
 
Access site injury requiring intervention, both venous and arterial
 
 
 
Utility Measures         
 
Length of hospital stay
 
Length of ICU stay
 
Use of ECMO, including either pre- or post-treatment initiation and duration
 
Time to extubation, if intubated
 
Discharge location
 
 
 
			
Severity of Adverse Event:	
 
Mild: No limitation of usual activities, no therapy or only symptomatic therapy required to treat the injury or illness
 
Moderate: Some limitation of usual activities or specific therapy is required
 
Severe: Inability to carry out usual activities, hospitalization, emergency treatment, life
 
			
Site activation	threatening events, or death The date the site receives approval from the Sponsor to begin enrolling in the study			
SILE ACTIVATION	The date the site receives approvalition the sponsor to begin enrolling in the study.			

Study Title: **FL**owTriever for **A**cute **M**assive Pulmonary **E**mbolism (FLAME)

Statistical Analysis Plan

Version 3.0

December 6, 2020

NCT Number: 04795167

Study Title: **FL**owTriever for **A**cute **M**assive Pulmonary **E**mbolism (FLAME)

Statistical Analysis Plan

Version 3.0

Name of Study Device: FlowTriever® Retrieval/Aspiration System

Protocol No.: 20-001

Study Phase: Observational, non-Interventional

CONFIDENTIALITY STATEMENT

This Statistical Analysis Plan and all attachments are considered confidential information. The contents must not be disclosed, unless authorized in writing by Inari Medical, except that this document may be disclosed to the appropriate Institutional Review Board (IRB) with similar requests for maintenance of confidentiality. All data and study results are similarly subjected to the same disclosure restrictions as the investigational plan, as stated above. All copies of this analysis plan remain the property of Inari Medical.

Version 3.0

Approval

This document has been reviewed and approved by:					
[name]					
Director, Head of Biostatistics and Programming	Signature	Date			

Version 3.0

Table of Contents

1.	Des	cription of Study Objectives	5
2.	Stud	ly Design	5
	2.1.	Primary Objectives	
	2.2.	Primary Endpoint	5
	2.3.	Secondary Endpoints	6
3.	Ana	lysis Populations	7
	3.1.	FlowTriever Arm	7
	3.2.	Context Arm	7
4.	Inco	mplete Date Handling and Missing Data	7
5.	Stat	istical Methods and Analysis	8
	5.1.	Sample Size	8
	5.2.	Derivation of Performance Goal	8
	5.3.	Primary Endpoint Analysis	10
	5.4.	Secondary Endpoint Analysis	10
	5.5.	Interim Analysis	11
	5.6.	Context Arm Analysis	11

Version 3.0

LIST OF ABBREVIATIONS AND DEFINITIONS

Abbreviation	Term	
AC	Anticoagulation	
BARC	Bleeding Academic Research Consortium	
CEC	Clinical events committee	
CPR	Cardiopulmonary resuscitation	
ECMO	Extracorporeal membrane oxygenation	
FLAME	FlowTriever for Acute Massive Pulmonary Embolism	
FT	FlowTriever	
GLM	Generalized linear models	
ICU	Intensive care unit	
IV	Intravenous	
PE	Pulmonary embolism	
PG	Performance Goal	
SAP	Statistical Analysis Plan	

Version 3.0

1. Description of Study Objectives

The primary objective of the FLAME observational study is to evaluate treatment outcomes of patients diagnosed with high-risk pulmonary embolism who have received treatment with the FlowTriever System (FlowTriever Arm) compared to an established performance goal (PG).

In addition to the primary objective, outcomes of patients diagnosed with high-risk (massive) pulmonary embolism who have received treatment with other (non-FlowTriever) therapies will also be analyzed.

2. Study Design

The FLAME study is a prospective, multicenter, non-randomized, parallel group, observational study of subjects with high-risk pulmonary embolism concurrently enrolled in the FlowTriever, Context, and Prior Therapy Arms of the study. FlowTriever Arm patients will be the primary population utilized to evaluate the study Primary and Secondary Endpoints for study success. These endpoints will also be evaluated in the Context Arm population in a descriptive manner and will not be used to determine study success.

2.1. Primary Objectives

To compare the treatment outcomes for patients who received FlowTriever against a historical performance goal. The treatment outcomes are assessed during a patient's in-hospital period for the index treatment of the high-risk pulmonary embolism.

2.2. Primary Endpoint

In-hospital composite endpoint of:

- All-cause mortality
- Bailout to an alternative thrombus removal strategy
- Clinical deterioration
- Major bleeding, BARC 3b/3c/5a/5b definition

Table 1: Primary Endpoint Definitions

Primary Endpoint Definitions	Bailout to an alternate thrombus removal strategy	Need for mechanical circulatory support or another thrombus removal strategy after the primary treatment strategy was initiated. The additional treatment strategy was not an a priori part of the original treatment plan (conceived beforehand). All bailout events will be adjudicated by the CEC.			
	Clinical Deterioration	 Need for CPR Need to start IV vasopressors to keep systolic blood pressure > 90 mmHg in a previously normotensive patient Need for mechanical ventilation in a previously spontaneously breathing patient Need for noninvasive positive pressure ventilation in a patient previously on nasal cannula 			
	Major Bleeding, BARC 3b/3c/5a/5b	 3b: Overt bleeding plus hemoglobin drop of ≥ 5 g/dL (provided hemoglobin drop is related to bleed); cardiac tamponade, bleeding requiring surgical intervention for control (excluding dental/nasal/skin/hemorrhoid); bleeding requiring intravenous vasoactive agents 3c: Intracranial hemorrhage (does not include microbleeds or hemorrhagic transformation, does include intraspinal), subcategories confirmed by autopsy or imaging or lumbar puncture, intraocular bleed compromising vision. 5a: Probable fatal bleeding; no autopsy or imaging confirmation but clinically suspicious 5b: Definite fatal bleeding; overt bleeding or autopsy or imaging confirmation 			

2.3. Secondary Endpoints

Secondary endpoints include safety endpoints as well as utility measures which will be assessed in the FlowTriever Arm. Details of the secondary endpoints are provided in **Table 2** below. These endpoints will also be evaluated in the Context Arm population in a descriptive manner and will not be used to determine study success.

Table 2: Secondary Endpoint Definitions

Secondary	Secondary Safety Endpoints		
Endpoints	•	Frequency of each primary endpoint composite component	
	•	Frequency of stroke (ischemic or hemorrhagic)	
	•	Frequency of device-related complications	

Version 3.0

• Access site injury requiring intervention, both venous and arterial

Utility Measures

- Length of hospital stay
- Length of ICU stay
- Use of ECMO, including either pre- or post-treatment initiation and duration
- Time to extubation, if intubated
- Discharge location

3. Analysis Populations

3.1. FlowTriever Arm

Up to 71 subjects will be enrolled in the FlowTriever Arm. FlowTriever Arm subjects are defined as those subjects where FlowTriever is used as the primary treatment for pulmonary embolism.

An interim analysis is planned for the first 50 subjects enrolled into the FlowTriever Arm. Based upon the interim analysis (as described in **Section 5.5**), a decision will be made whether to continue enrollment.

3.2. Context Arm

Subjects with high-risk pulmonary embolism who are treated with non-FlowTriever therapies (as the primary treatment for PE) will be enrolled concurrently with subjects in the FlowTriever arm. Context-arm therapies may include but are not limited to; thrombolysis (either systemic or catheter directed), anticoagulation, surgical thrombectomy, and non-FlowTriever percutaneous thrombectomy. The Context Arm enrollment will have at least 1:1 ratio as compared with the FlowTriever Arm, therefore at least 71 subjects would be in the Context Arm population.

3.3. Prior Therapy Arm

Data collection for Prior Therapy Arm subjects will include information surrounding the PE treatment, progression to High-Risk PE, and patient course through hospital discharge. Safety data will also be collected, but not CEC adjudicated or analyzed as outlined for the FlowTriever and Context Arm subjects. Subjects receiving prior advanced treatment for low/intermediate-risk PE in the same hospital setting as a second treatment for high-risk PE likely have a different profile than those receiving advanced care for the first time after diagnosis of high-risk PE, and therefore should be looked at separately. In the spirit of the AHA guidelines for trial design in this patient population, data will be collected to ensure representation of this smaller yet significant group of high-risk PE patients and will be reported in a descriptive manner.

4. Incomplete Date Handling and Missing Data

Incomplete dates will be handled with the following imputation rules:

Version 3.0

- 1. If day is missing but month and year are present, the day will be set to the first date of the month.
- 2. If both day and month are missing but year is present, then January 1st will be used as imputed value.
- 3. If year is missing then the date is considered missing. In general, missing data points are not imputed.

Other missing data will not be imputed.

5. Statistical Methods and Analysis

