## 6.1.6 Study Exit

Subjects may be exited from the study if they are deceased prior to discharge. As this study is only looking at outcomes through hospital discharge, it is not expected that subjects will be lost to follow-up. Subjects who remain in-hospital (from the index hospitalization for high-risk PE) for  $\geq$  45 days after the Primary Treatment for high-risk PE will be exited from the study at that time, as the study is considering acute outcomes for the treatment of high-risk pulmonary embolism.

Study Exit for all subjects, regardless of reason, will be documented on a Study Exit form in the study record.

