5.4. Secondary Endpoint Analysis

Secondary Endpoints include both Secondary Safety Endpoints and Utility Measures as listed below: Secondary Safety Endpoints

- Frequency of each primary endpoint composite component
- Frequency of Stroke (ischemic or hemorrhagic)
- Frequency of device-related complications
- Access site injury requiring intervention, both venous and arterial

Utility Measures

- Length of hospital stay
- Length of ICU stay
- Use of ECMO, including either pre- or post-treatment initiation and duration
- Time to extubation, if intubated
- Discharge location

Descriptive statistics will be used for secondary endpoints for both the FlowTriever Arm and Context Arm populations. Continuous variable will report min, max, mean, SD, IQR, Q1, Q3 etc. as deemed

^{*}Operative mortality was reported. Only patients in refractory shock were included in the analysis.

[†]All patients died within 15 hours of the procedure.

Version 3.0

appropriate. Categorical variable will report frequency counts and percentage. Time-to-event variable may be reported with Kaplan-Meier and/or Cox proportional hazards model estimates.

Additional exploratory analyses on secondary endpoints may include confounder adjustment in generalized linear models (GLMs) and may be specified in separate SAPs.

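### SAP section 4 imputes partial dates to the 1st of the month or 1 January without exempting dates inside the index stay, which distorts any in-hospital duration built on one (minor)

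*SAP*

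**What the plan says.** SAP section 4 has three rules for incomplete dates. Rule 1: "If day is missing but month and year are present, the day will be set to the first date of the month". Rule 2: "If both day and month are missing but year is present, then January 1st will be used as imputed value". Rule 3 leaves a date missing when its year is missing. The section adds "In general, missing data points are not imputed" and closes by excluding imputation of other missing data. The rules do not separate start dates from end dates, or medical-history dates from in-hospital dates. They set no limit at admission, treatment, discharge or death. Protocol section 7 has no date rule that would override them.

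The utility measures in SAP section 2.3 include length of hospital stay, length of ICU stay, time to extubation and "Use of ECMO, including either pre- or post-treatment initiation and duration". Protocol Table 10 defines hospital stay as "Time from admission to the hospital for pulmonary embolism treatment until discharge from the hospital post-treatment", with death as the end point for subjects who die in hospital. For ICU stay it adds "Multiple ICU stays within the same hospital admission (index hospitalization for high-risk PE) will be recorded", so one subject can contribute several date pairs. Under Protocol section 6.1.6, subjects still in hospital 45 days or more after Primary Treatment "will be exited from the study at that time, as the study is considering acute outcomes".

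SAP section 5.4 plans descriptive statistics for these measures, including minimum and maximum, and adds: "Time-to-event variable may be reported with Kaplan-Meier and/or Cox proportional hazards model estimates".

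**The concern.** Rules 1 and 2 can only move a date back or leave it unchanged. That does little harm to a medical-history date well before admission. It matters when the date is one end of an interval measured in days. An end date moved back shortens the interval or takes it below zero; a start date moved back lengthens it. The errors have a known direction, and their size is set by the calendar, not by the patient.

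At stake are the reported summaries of the four durations and any Kaplan-Meier or Cox estimates on them. A negative stay would probably be seen in the reported minimum, although the SAP does not say what to do with it. A true 7-day stay recorded as 20 days would not stand out.

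**Working it through.** The plan gives no figure to reproduce, so the check applies the rules to known intervals.

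**Inputs.** Rules 1 and 2 are from SAP section 4, the stay definitions from Protocol Table 10, the 45-day limit from Protocol section 6.1.6, and the arm size of 71 from SAP section 3.1. The documents give no expected length of stay and no calendar, so these are assumed: start dates uniform over 2021-2022 (730 days), true durations k of 3, 7, 14, 21 and 44 days, and one partial date per duration. Table 10 does not define ECMO duration or time to extubation; both are taken as running from a recorded start date to a recorded end date.

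**One case.** A true stay from 10 to 20 March lasts 10 days.
- Discharge day missing: 1 March − 10 March = −9 days.
- Admission day missing: 20 March − 1 March = 19 days.
- Discharge day and month missing: 1 January − 10 March = −68 days.
- Admission day and month missing: 20 March − 1 January = 78 days.

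A stay that crosses a month end, 28 March to 7 April (also 10 days), becomes 4 days with the discharge day missing and 37 days with the admission day missing.

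**Average error, day missing.** The error is (day of month − 1). Over a 365-day year its sum is 7 × 465 + 4 × 435 + 378 = 5,373, so the mean is 5,373 / 365 = 14.72 days, whatever the true duration. The imputed date is correct only when the true day is the 1st: 12 / 365 = 3.3% of dates.

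**By true duration.** Let a be the start and b = a + k.
- End day missing: recorded duration = first-of-month(b) − a.
- Start day missing: recorded duration = b − first-of-month(a).
- The first is negative when a and b fall in the same month and a is after the 1st. For k = 3 to 21 that is (365 − 12(k + 1)) / 365 of dates. For k = 7: (365 − 96) / 365 = 269 / 365 = 73.7%.

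| True duration k (days) | End day missing: negative | End day missing: mean | Start day missing: mean | Start day missing: ratio to truth |
|---|---|---|---|---|
| 3 | 86.8% | −11.7 | 17.7 | 5.9 |
| 7 | 73.7% | −7.7 | 21.7 | 3.1 |
| 14 | 50.7% | −0.7 | 28.7 | 2.1 |
| 21 | 27.7% | 6.3 | 35.7 | 1.7 |
| 44 | 0% | 29.3 | 58.7 | 1.3 |

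**Would a bound at hospital admission be enough?**
- Partial discharge date, recorded duration = max(first-of-month(b), a) − a: negatives disappear, but for k = 7 the result is 0 days for (365 − 12 × 7) / 365 = 281 / 365 = 77.0% of dates.
- Partial start date of an ICU stay that begins one day after admission: the error is at most 1 day, with mean 1 − 12 / 365 = 0.97 days.
- Partial admission date: a floor at admission has nothing to work from.

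**Effect on a reported mean.** One partial date shifts a mean over n subjects by 14.72 / n on average: 0.21 days for n = 71. The number of ECMO or intubated subjects is not given. If it were 20, 10 or 5, the shift would be 0.74, 1.47 or 2.94 days.

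**The case against.** The strongest reply is that this will hardly ever happen. The footnotes to Protocol Table 3 require date and time for the treatment decision and for treatment initiation, and start and stop dates and times for anticoagulants and thrombolytics. Monitors check that data are complete (Protocol section 6.7), and queries must be answered (section 6.10.1). Nothing suggests that admission, discharge or death dates would lack a day. Partial dates are likelier in medical history, where the rule is reasonable. This stands, and it is the main reason the point is minor. It does not remove the point: data come from retrospective chart review (section 6.1.3.1), and section 4 still governs any partial date that remains.

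Second, many of the errors reveal themselves. With the discharge day missing, a true 3-day stay comes out positive but wrong for only about 6.6% of dates; for a true 7-day stay it is about 20%. This also stands for short stays with a partial end date. It does not cover partial start dates or longer stays.

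Third, a floor at hospital admission nearly removes the error for ICU, ECMO or intubation start dates soon after admission. This is correct, as the 0.97-day result shows, so it would be wrong to say that bounds are useless. They do not repair partial end dates or a partial admission date.

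A reader might also infer that section 4 contradicts its own policy, since it says "In general, missing data points are not imputed". The text does not support so firm a reading. The sentence follows the missing-year rule, and dates can be read as the deliberate exception. At most it shows that leaving a duration missing would fit the section's general approach.

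**Conclusion.** The point holds as a minor one. Section 4 states a rule that gives wrong values when applied to a partial start or end date of hospital stay, ICU stay, ECMO or intubation. The direction follows from the rule alone. The 14.7-day average and the percentages rest on the assumed calendar and durations, and all are conditional on a partial in-stay date occurring. How many will occur is unknown and probably small.

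Three stronger readings are not supported:
- **That the primary result is at risk.** The primary endpoint is an in-hospital composite, adjudicated by the CEC and tested as a proportion against 32%. It uses no duration.
- **That ECMO would be misclassified as before or after treatment.** The CEC adjudicates circulatory support added after treatment began as possible bailout, and no passage has an imputed date decide it.
- **That every incomplete date is imputed.** Rule 3 leaves a date without a year missing, and a date that truly falls on the 1st is unchanged by rule 1.

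**What to change.** Add to SAP section 4 that rules 1 and 2 do not apply to start or end dates used to calculate length of hospital stay, length of ICU stay, ECMO duration or time to extubation. If a query to the site does not resolve such a date, treat the duration as missing and report the number missing for each measure. Leave the rules as they are for all other dates, including adverse-event and medication dates, where no harm has been shown.

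The cost is two or three sentences and no new data. The downside is that a few durations may be missing, which could be noticeable in a small ECMO or intubated subset.
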